Investigational Device	UVA Model Predictive Control Artificial Pancreas (RocketAP) with and without use of the Bolus Priming System (BPS)
Objectives	The purpose of this study is to show the safety and feasibility of a new fully automated AP controller with and without the Bolus Priming System
Study Design	A randomized cross-over trial assessing glycemic responses to a fully automated AP system using two approaches: 1) using the Bolus Priming System (which detects shifts in glucose level to trigger a priming dose of insulin) 2) without the Bolus Priming System We will also have structured meal and exercise challenges of the fully closed loop system.
Number of Sites	One
Endpoint	The primary outcome will be time in range 70-180 mg/dL for a 24-hour period.
Population	Key Inclusion Criteria 
• Age 18 and \leq65 years of age• Clinical diagnosis, based on investigator assessment, of type 1 diabetes for at least one year• Currently using insulin for at least six months• Currently using insulin pump for at least three months
Sample Size	
• Pilot Study: complete a minimum of 2-3 participants• Main Study: complete up to 20 participants
Treatment Groups	Randomized crossover: Participants will be randomized to the order that they experience the use of the BPS in fully automated closed loop (FCL) (for 24 hours each, with a 24-hour washout in between): 1) with the BPS active, 2) without BPS.
Participant Duration	Pilot Study: Participants will be admitted to a local hotel or rental house for up to approximately 24 hours and will have a dinner with the RocketAP without the BPS Main Study: Participants will be admitted to a local hotel for approximately 96 hours.

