152 completing a minimum of 2-3 participants. This admission will be about 24 hours at a hotel/rented
153 house. Enrollment in the Main Study will proceed with the goal of completing 20 participants.

154 **1.3.1 Study Hardware/Software**

155 The study itself will involve use of the DiAs prototyping platform (MAF 2109), connected to a
156 Tandem t:AP research pump and a Dexcom G6 sensor, and implementing RocketAP with and
157 without BPS. Upon arrival at the hotel, participants will be instructed in how to use the Tandem
158 research pump as well as the UVa AP system, including stopping the system.

159 **1.3.2 Timing of UVa Artificial Pancreas Use**

[figure not shown]
160 The participants will arrive to hotel the evening before starting the experimental system to allow
161 for a settling of blood glucose in an unfamiliar environment. The next morning, participants will
162 be connected to a Tandem research pump connected to the UVa DiAs platform and their Dexcom

CLINICAL PROTOCOL

163 G6 Transmitter will be linked with DiAs. Participants will then be taught how to use DiAs in this
164 configuration. The research pump will be programmed with the individual's usual insulin
165 parameters. Once started, the participants will have their blood sugar managed through this system
166 during the entirety of the time at hotel.

167 1.3.3 Study Controller Sessions

168 *Order and timing of controller sessions:* During the hotel stay, participants will have two separate
169 24-hour periods during which they will receive FCL control with and without the BPS active.
170 These will be separated by a 24-hour challenge period which will involve further challenges. The
171 timing and potential order of these sessions is shown in Figure 1.

[figure not shown]

172

173 Figure 1: Timeline and randomized order of the Study Controller Sessions

174 During these 24-hour periods participants will be followed for the experimental meals as part of
175 the Study Controller Sessions to compare blood glucose control with and without the BPS (Figure
176 1). The study meals and activities will be standardized between study sessions (see Figure 2).

CLINICAL PROTOCOL

177

178 Figure 2: Timeline of Study Controller Sessions and Study Meals and activities. There will be two identical 24-
179 hour periods (FCL1 in green and FCL2 in orange), separated by a 24-hour challenge period (FCL1 in green-hatched)

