180 that will first involve the BPS activation assignment the participant was randomized to (the treatment approach used
181 in FCL1) and then involve the alternate assignment (the treatment approach to be used in FCL2), with the system
182 switch at the end of the challenge day. Arrows represent meals with Blue Arrows representing meals in which the
183 participants are using their personal devices.

184 The primary outcome will compare the percent time CGM is between 70 and 180 mg/dL during
185 daytime for FCL1 and FCL2 sessions with and without BPS. During the time between arrival at
186 the hotel and being started on the experimental system, participants will use their home diabetes
187 management approach, including insulin dosing via normal carbohydrate announcement. Starting
188 the first morning of the study (Day 2 of study), study staff who will be present will include nursing
189 staff and technical staff; a study physician will be available either on-site or nearby off-site at all
190 times. Hyperglycemia and hypoglycemia treatment protocols will be followed per guidelines. We
191 anticipate more significant cases of hyperglycemia during meals on the study system because of
192 the lack of carbohydrate announcement; participants will be encouraged to drink large amounts of
193 non-caloric beverages, particularly after these meals. UVA CDT study staff will monitor CGM
194 output continuously and manage glucose control issues. At the end of the hotel stay, the participant
195 will return to their home insulin management.

196 1.4 Study Device Download

197 Before discharge from the hotel, all study devices will be turned in to study staff for device
198 download, and the participants will return to their usual diabetes management.

199 1.5 Study System Issues

200 If the CGM signal becomes unavailable for more than 20 minutes consecutively, closed loop will
201 not operate to automatically adjust insulin. If the CGM is not connected, the system will revert to
202 usual function of the pump and deliver insulin with the insulin dosing parameters programmed in

CLINICAL PROTOCOL

203 the system for that individual. Resumption of closed-loop control will occur automatically once
204 CGM signal is available again.

205 If the study system is unable to maintain pump connectivity, the pump will automatically revert to
206 pre-programmed basal insulin delivery after 30 minutes without any need for instruction from the
207 user.

CLINICAL PROTOCOL

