CLINICAL PROTOCOL

666 **7.8 Admission Discharge**

667 Discharge will be at approximately 1 pm. Discharge criteria is CGM value 80-300 mg/dL with
668 stable trend and ketones <=0.6 mmol/L. If the CGM values are above 300 mg/dL and ketone values
669 are >0.6 mmol/L, the study team will check the insulin pump infusion site and correction insulin
670 will be administered per study physician judgement via the subject's insulin pump. A qualified
671 clinical study team member (e.g. MD, NP, PA, CDE) will assess and discuss the transition back to
672 usual care with the study participant.

673 Participants will be asked to continue monitoring ketone levels for 24-48 hours after the hotel
674 admission if ketones were >0.6 mmol/L prior to discharge. Urine ketone supplies may be provided
675 for this testing.

676 All study equipment will be returned at the time of study end. Per investigator discretion, a
677 participant may wear home the study CGM device in use and will be requested to return the study
678 transmitter.

679 **7.9 Visit 5: Post Admission Check-In Visit**

680 Approximately 24-48 hours after the hotel admission, the study team will contact the participant
681 via phone/email/text to assess adverse events, adverse device effects, and device issues.

682 **7.10 Medical Monitor Review**

683 At the conclusion of the Main Study, the medical monitor will review the data as referenced in
684 section 8.3.

CLINICAL PROTOCOL

685 **Chapter 8 Medical Monitor Review**

686 **8.1 Medical Monitor Study Safety Data Review**

687 The Medical Monitor will be provided all adverse event data for review to assess safety. The
688 Medical Monitor will review data related to individual stopping criteria as detailed in the study
689 protocol.

690 **8.2 Medical Monitor Main Study Safety Data Review**

691 A Medical Monitor will review compiled safety data at the conclusion of the trial. In addition, the
692 Medical Monitor will review all DKA and severe hypoglycemia irrespective of relatedness to study
693 device use, and all serious events (including UADEs) related to study device use at the time of
694 occurrence. The Medical Monitor also will be informed of any ADEs not meeting criteria for a
695 UADE if the Study PI requests the Medical Monitor review. The Medical Monitor can request
696 modifications to the study protocol or suspension or stoppage of the study if deemed necessary
697 based on the totality of safety data available.

CLINICAL PROTOCOL

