1145 As a early exploratory Study, the goal will be to complete up to 20 participants in the main study
1146 to provide data from a variety of individuals. This number was chosen out of feasibility and not
1147 from a formal power calculation. (The Pilot Study for this proposal will assess ease of system and
1148 will be completed in a minimum of 2-3 individuals prior to the beginning of the Main Study.) With
1149 N=20 and our randomized crossover design (allowing for paired comparison), we can hope to detect a
1150 minimum effect size of 0.66 at a power of 80%. Based of prior FCL study, the standard deviation of daytime
1151 TIR is approximately 12%, leading to a detectable difference in daytime TIR of 8%.

1152 **13.3 Outcome Measures**

1153 **13.3.1 Primary Efficacy Endpoint**

1154 The study design allows for multiple comparisons of blood glucose control during the study meals
1155 and exercise sessions, with for the primary comparison of interest being between the RocketAP
1156 with and without BPS. Our primary endpoint is CGM time-in-range 70-180 mg/dL for the daytime
1157 period 6 am – 12 am when on each treatment modality (BPS vs. no BPS).

1158 **13.3.2 Secondary Outcomes**

1159 Each admission is separated into windows of analysis:

- 1160 • The entirety of the admission (24h: 4pm to 4pm)
- 1161 • The 4 hours following each of the meals.
- 1162 • The overnight period (12 am to 6 am)

1163 For each of these periods we will compute the following outcomes:

- 1164 • Number of hypoglycemia events defined as at least two consecutive CGM values
1165 <70mg/dL or a hypoglycemia treatment (two events separated by less than 30 minutes are
1166 counted as one).
- 1167 • Percent CGM time <70 mg/dL
- 1168 • Percent CGM time between 80-140mg/dL
- 1169 • Percent CGM time between 70-180mg/dL
- 1170 • Percent CGM time >180 mg/dL
- 1171 • Percent CGM time >250 mg/dL
- 1172 • Units of insulin injected
- 1173 • Area under the curve when accounting for starting BG
- 1174 • Low Blood Glucose Index
- 1175 • High Blood Glucose Index
- 1176 • CGM coefficient of variation
- 1177 • Mean CGM

CLINICAL PROTOCOL

1179

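### The 4 pm to 4 pm full-session window (13.3.2) does not fit a morning system start and discharge at about 1 pm, so FCL1 and FCL2 would be summarised over unlike hours

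*Combined protocol and SAP*

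**What the plan says.** - **Analysis window.** Section 13.3.2 lists, as the first window for the secondary outcomes, "The entirety of the admission (24h: 4pm to 4pm". The outcomes computed in it include units of insulin, number of hypoglycemia events and an area under the curve. No scaling by hours observed is stated.
- **Discharge.** For the Main Study, section 7.8 states "Discharge will be at approximately 1 pm".
- **Devices.** Section 1.4 states "Before discharge from the hotel, all study devices will be turned in to study staff for device" download, after which usual management resumes. Section 7.8 adds one exception: at investigator discretion a "participant may wear home the study CGM device in use and will be requested to return the study" transmitter.
- **Timeline.** The synopsis describes a four-night stay and gives the two conditions "for 24 hours each, with a 24-hour washout in between". Section 1.3.2 has evening arrival, connection to the study system the next morning, and use of that system for the rest of the stay. Section 1.3.3 places that first morning on Day 2.
- **Sessions.** The Figure 2 legend says "There will be two identical 24"-hour periods, separated by the challenge period, with the "switch at the end of the challenge day". Session clock times are in Figures 1 and 2, which are not shown in the text available for this review.
- **Sufficiency rule.** Section 13.3.4 computes an outcome only if at least 80% of the window's CGM values remain after data treatment. Section 13.3.3 removes CGM values within 2 h either side of a recorded occlusion.

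**The concern.** FCL2 is the last of three consecutive 24-hour periods, so it ends on the day of discharge. A window closing at 4 pm that day closes about 3 h after the participant has left and returned the pump. FCL1 has no such limit, because the participant is still in the hotel at 4 pm on Day 3. The plan therefore either compares a shorter FCL2 with a full FCL1, or uses a clock label that does not match its own sessions and mixes challenge-day hours into FCL1.

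The outcomes most exposed are those that accumulate with time. Percent-time outcomes, means and indices are not scaled by the shortfall, but they would still describe different clock hours in the two sessions. If the window is left as written, someone will have to choose the hours after the data are in.

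**Working it through.** **Inputs.** Window 4 pm to 4 pm (13.3.2). Discharge hour D on Day 5, about 13:00 (7.8), taken as noon to 2 pm for a range (assumption). Evening arrival on Day 1, system on from the morning of Day 2 (1.3.2, 1.3.3). Four nights and three 24-hour periods (synopsis, 1.3.3). Session start hour S is not given in the text and is varied below.

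**1. The plan's own figure.** 4 pm to midnight is 8 h and midnight to 4 pm is 16 h: 8 + 16 = 24 h, as stated.

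**2. Calendar.** Four nights from Day 1 put departure on Day 5. FCL1 runs Day 2 to 3, the challenge period Day 3 to 4, and FCL2 Day 4 to 5.

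**3. Window applied literally.** FCL1: Day 2 16:00 to Day 3 16:00 = 24 h on the system. FCL2: Day 4 16:00 to discharge = 8 + D.
- D = 13: 21 h, 21/24 = 87.5%
- D = 12: 20 h, 83.3%
- D = 14: 22 h, 91.7%

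This holds for any S from the Day 2 morning to 4 pm, because the system stays on until discharge.

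**4. Do three full sessions fit?** From hour S on Day 2 to 13:00 on Day 5 is 72 + (13 − S) h, and 72 h are needed. S = 8 gives 77 h and S = 13 gives 72 h. S = 16 gives 69 h, which is 3 h short. Identical 24-hour sessions therefore require a start by 1 pm.

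**5. What the window captures, by start time (D = 13).** Opening hours dropped from each session = challenge-day hours taken into FCL1 = 16 − S. FCL2 session hours inside the window = 8 + min(S, 13). FCL2 daytime hours (6 am to midnight) = (24 − S) + (min(S, 13) − 6).

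| Start S (assumed) | Opening hours dropped, each session | Challenge-day hours in FCL1 window | FCL2 session hours in window | FCL2 daytime hours of 18 |
|---|---|---|---|---|
| 8 am | 8 | 8 | 16 | 18 |
| noon | 4 | 4 | 20 | 18 |
| 1 pm | 3 | 3 | 21 | 18 |
| 4 pm | 0 | 0 | 21 | 15 |

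With noon discharge the last column becomes 17/18 for a 1 pm start and 14/18 (77.8%, below 80%) for a 4 pm start. Starts by noon keep 18/18.

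**6. The 80% rule.** 0.80 × 24 = 19.2 h. With no other CGM loss, 21 h passes with 1.8 h to spare. One occlusion removes up to 2 + 2 = 4 h. FCL2 then keeps 17/24 = 70.8% and fails, while FCL1 keeps 20/24 = 83.3% and passes. If the sensor is worn home, CGM coverage could reach 24 h, but the last 3 h would be off the study controller.

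**7. Totals.** At an assumed constant hourly rate, the FCL2 total is lower by 3/24 = 12.5% from hours alone (2/24 = 8.3% to 4/24 = 16.7% over the discharge range).

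**8. Effect on the BPS contrast.** Let δ be the shortfall in period 2. A participant with BPS first contributes τ + δ and one with BPS second contributes τ − δ. With n₁ and n₂ participants in the two orders, the mean is τ + δ(n₁ − n₂)/(n₁ + n₂). With equal orders the second term is zero and δ only widens the spread of the paired differences. The model in 13.1.1 (BPS status, HbA1c, gender) has no period term to remove it, and the Wilcoxon test expected for hypoglycemia counts takes no covariates.

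**The case against.** The strongest reply is that 4 pm to 4 pm is only a wrong label. The system starts in the morning, and three 24-hour periods from a Day 2 morning finish on the Day 5 morning, before discharge. Section 13.3.2 also speaks of 24-hour admissions, whereas the Main Study has a single longer one. On this reading no session data are lost and the primary endpoint is intact. The affected window serves secondary outcomes in an early exploratory study, and at most three of the twelve listed outcomes accumulate over time.

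Most of this stands, and it is the better reading of the text. It does not repair the plan. With a start by 1 pm, the written window still omits 3 h or more of each session and takes the same number of challenge-day hours into FCL1, while FCL2 has no challenge day after it. Those hours are normally under the same BPS state, because the switch comes at the end of that day, but they may include different meals or exercise.

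Four stronger inferences are tempting and are not supported:
- **That FCL2 data are actually cut to 21 h.** This needs the label to be applied literally or sessions to start after 1 pm. The second conflicts with the stated identical 24-hour periods.
- **That the BPS comparison is biased.** The shortfall follows period, and order is randomised in blocks of 4.
- **That the 80% rule always lets the shorter window through.** The rule applies after data treatment, and one occlusion can reverse the result.
- **That the stated length of stay is a further contradiction.** The synopsis says "Participants will be admitted to a local hotel for approximately 96 hours", but section 7.1 makes this an upper limit. An assumed 6 pm arrival to 1 pm on Day 5 is 96 − 5 = 91 h, which fits.

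**Conclusion.** The conflict between 13.3.2 and sections 7.8, 1.4 and 1.3.2 is in the text, and no passage resolves it. Read literally, FCL2 has about 21 of 24 h on the study system (20 to 22 h for discharge between noon and 2 pm) and FCL1 has 24 h. If sessions start by 1 pm, as the text best supports, both are complete but the window is displaced by 16 − S hours: 3 h for a 1 pm start, 8 h for an assumed 8 am start.

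The consequence is mainly period noise in insulin units, hypoglycemia counts and area under the curve if integrated, plus an uneven risk that FCL2 fails the 80% rule. The daytime primary endpoint is affected only if FCL2 ends after discharge.

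Confidence is high that the passages conflict. Which line is wrong cannot be settled without the session clock times in the figures. The 12.5% figure rests on a constant hourly rate.

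**What to change.** Reconcile 13.3.2 with 7.8 and the session timeline, before any outcome data are examined:
- Define the full-session window from the actual session start and BPS switch times. Use the same clock hours in FCL1 and FCL2, end before devices are removed, and exclude challenge-day hours.
- Compute insulin units, hypoglycemia events and any integrated area under the curve only over those common hours.
- Apply the same rule to the daytime primary endpoint only if the timeline shows FCL2 running past discharge.

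The cost is protocol and SAP wording and, at most, a slightly shorter common window. No procedures or participants are added.

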13.3.3 CGM data treatment

1180 • Saturated CGM values “High” and “Low” will be replaced by 401mg/dL and 39mg/dL
1181 respectively.

1182 • Any CGM gaps shorter than 1 hour will be interpolated
1183 • CGM data during recorded occlusion event will be removed from analysis as follow:
1184 any measurement less than 2h before or after the time of record will be removed.
1185 • CGM data following a pump/DiAs communication interruption >1h by less than 2h
1186 will be removed

1187

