CLINICAL PROTOCOL

459 **5.3 Study Insulin Pump**

460 The study team will be responsible for monitoring and managing the study insulin pump during
461 the hotel admissions. The participants may be provided a quick overview on its functionality to
462 understand the equipment.

463 **5.3.1 Study Insulin Pump Topics**

464 The study team will assist the participant in study pump infusion site initiation and will start the
465 participant on the study pump. The study pump will be programmed with the participant's usual
466 basal rates and pump parameters. The participant's personal pump will be removed. The
467 investigator may elect to use an existing personal pump infusion site at their discretion at the start
468 of the study.

469 The participant will be instructed on charging the pump, navigation through menus, bolus
470 procedures including stopping a bolus, etc.

471 **5.3.2 Other Issues**

472 The participant will be instructed to notify study staff if they experience any issues with the study
473 devices during the hotel admission. Staff will be present in the event that if insulin is delivered by
474 any means other than the study pump (e.g. injection of subcutaneous insulin via syringe in the
475 event of infusion site failure). If insulin is delivered by any means other than the study pump, the
476 study team will be instructed to turn off closed-loop mode for approximately four hours.

477 The participant will also be asked to alert the study clinical staff for technical issues with the
478 Tandem research pump and/or the DiAs system, including use of the study pump and study CGM
479 (open loop mode) during periods of component disconnections or technical difficulties.

480 A glucagon emergency kit will be available at the hotel once the investigational system is in place.

481 Glycemic Treatment Guidelines will be available for staff use during the study admissions.

482 **5.3.3 Optimization of Insulin Pump Settings**

483 Data-driven optimization of pump settings can occur any time prior to the hotel admission,
484 particularly if the participant contacts the study physician due to concerns about their pump
485 settings due to recurring hypo- or hyperglycemia. No pump settings changes can occur during
486 closed loop testing.

CLINICAL PROTOCOL

487 **Chapter 6 Pilot Study**

488 In order to optimize the flow of the study visits during the Main Study, we will perform a Pilot

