13.3.4 Outcome computation conditions

1188 Outcomes will only be computed if at least 80% of the analysis window CGM measurements (after data
1189 treatment) are available

1190

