13.6 Device Issues

1209 The following tabulations and analyses will be performed during time on the UVa AP systems to
1210 assess device issues:

1211 • Device malfunctions requiring study team contact and other reported device issues
1212 • % time CGM data available
1213 • % time with closed loop control

CLINICAL PROTOCOL

1214 **Chapter 14 Data Collection and Monitoring**

1215 **14.1 Case Report Forms and Device Data**

1216 The study data are collected through a combination of case report forms (electronic and paper) and
1217 electronic device data files obtained from the software and individual hardware components. These
1218 electronic device files and electronic CRFs are considered the primary source documentation.

1219 When data are directly collected in electronic case report forms, this will be considered the source
1220 data. Records will be maintained in accordance with ICH E6 and institutional regulatory
1221 requirements for the protection of confidentiality of participants.

1222 **14.2 Study Records Retention**

1223 Study documents should be retained for a minimum of 2 years after the last approval of a marketing
1224 application in an ICH region and until there are no pending or contemplated marketing applications
1225 in an ICH region or until at least 2 years have elapsed since the formal discontinuation of clinical
1226 development of the investigational product. These documents should be retained for a longer
1227 period, however, if required by local regulations. No records will be destroyed without the written
1228 consent of the sponsor, if applicable. It is the responsibility of the sponsor to inform the investigator
1229 when these documents no longer need to be retained.

1230 **14.3 Protocol Deviations**

1231 A protocol deviation is any noncompliance with the clinical trial protocol, Good Clinical Practices
1232 (GCP), or procedure requirements. The noncompliance may be either on the part of the participant,
1233 the investigator, or the study site staff. As a result of deviations, corrective actions may be
1234 developed by the site and implemented as appropriate. Major deviations will be reported to the
1235 IRB-HSR within 7 calendar days of when the study team becomes aware of the event.

CLINICAL PROTOCOL

1236 **Chapter 15 Ethics/Protection of Human Participants**

1237 **15.1 Ethics Standard**

1238 The investigator will ensure that this study is conducted in full conformity with Regulations for

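### One occlusion recorded in the middle of the daytime window leaves that session without a primary outcome, while some off-controller CGM is kept

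*Combined protocol and SAP*

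**What the plan says.** - **Primary endpoint (13.3.1):** CGM time in 70-180 mg/dL from 6 am to midnight, 18 h, in each BPS state. The hypotheses (13.1.1) and the sample size (13.2) also use daytime.
- **Occlusions (13.3.3):** "any measurement less than 2h before or after the time of record will be removed". Only gaps shorter than 1 h are interpolated, so this hole is not filled.
- **Interruptions (13.3.3):** the data removed are "CGM data following a pump/DiAs communication interruption >1h by less than 2h".
- **Availability (13.3.4):** "Outcomes will only be computed if at least 80% of the analysis window CGM measurements (after data" treatment) remain. The count is therefore made after the removals.
- **When automated control is off:** with lost pump connectivity the pump falls back to "pre-programmed basal insulin delivery after 30 minutes without any need for instruction from the" user (1.5). After insulin given outside the study pump, such as a syringe dose for a failed infusion site, the "study team will be instructed to turn off closed-loop mode for approximately four hours" (5.3.2).
- **Analysis (13.1.1, 13.2):** repeated-measures ANOVA on up to 20 participants, a number set by feasibility. A mixed model is considered only if more than 3 subjects have a missing admission.
- **Closed-loop time (13.6):** its percentage is tabulated, but no rule ties it to the endpoint.

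**The concern.** Two things sit badly together.

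First, the occlusion rule can take 4 h and the availability rule tolerates 3.6 h. A single device event of a foreseeable kind can therefore cancel a session's primary outcome, although about 14 h of daytime CGM remain. The void comes from the plan's own removals and not from lost sensor signal, so the statement that few missing values are expected does not answer it.

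Second, the removals do not follow the periods when the assigned controller is off. As worded, the 2 h after a long interruption go and the interruption stays. The roughly 4 h with closed loop off after non-pump insulin has no rule at all. CGM from those periods counts as time in range for the BPS state in force.

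At stake are precision in a study with few pairs to spare, and a clear account of what the daytime TIR contrast measures.

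**Working it through.** **The plan's own figure.** Section 13.2 gives an effect size of 0.66 at 80% power with N = 20 paired, and 8% for an SD of 12%. A paired t-test (noncentral t, 19 df, two-sided 0.05 assumed because alpha is not stated) gives 0.660, and 0.660 × 12 = 7.93 points. The figure reproduces. It treats 12% as the SD of the paired difference.

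**1. Occlusion against the 80% rule.**
- Allowance: 20% × 18 h = 3.6 h.
- A record at least 2 h from every window edge removes 4 h: 14/18 = 77.8%, which fails.
- A record at distance d < 2 h from an edge removes 2 + d h. This exceeds 3.6 h when d > 1.6 h.
- A 4 pm to 4 pm session (13.3.2) splits the daytime into 8 h and 10 h. Voiding record times are (8 − 3.2) + (10 − 3.2) = 11.6 h, and 11.6/18 = 64%. With a 1 pm changeover (the discharge time in 7.8) the split is 11 h and 7 h, and 7.8 + 3.8 = 11.6 h again.
- On the 24 h window the same event leaves 20/24 = 83.3%, which passes.

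**2. Cost of lost pairs.** This assumes that the RANOVA uses complete pairs; the documents do not say how an uncomputed outcome enters it.

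| Pairs | Detectable effect | × 12 (points) | Power at 8 points |
|---|---|---|---|
| 20 | 0.660 | 7.93 | 80.7% |
| 19 | 0.680 | 8.16 | 78.5% |
| 18 | 0.701 | 8.41 | 76.0% |
| 17 | 0.724 | 8.69 | 73.3% |

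Three lost pairs is the most before 13.1.1 considers a mixed model.

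**3. Interruption of L hours, L > 1.** With 2 h removed afterwards, 16 h are kept. Fallback basal starts after 30 minutes, so about L − 0.5 h of the kept data are on fallback basal.
- L = 1 h (limiting case): 0.5/16 = 3.1%.
- L = 2 h: 1.5/16 = 9.4%.
- If TIR in that stretch changed by the full 100 points, the 20-pair mean would move by 3.1/20 = 0.16 or 9.4/20 = 0.47 points.

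**4. Closed loop off for about 4 h after non-pump insulin.**
- No occlusion record: nothing is removed, and 4/18 = 22.2% of the window is off-controller. The 20-pair mean moves by at most 22.2/20 = 1.1 points.
- Occlusion recorded mid-window: the session is already void under step 1, so nothing reaches the primary endpoint.
- Occlusion recorded near an edge: the session survives, and at most about 2 h of off-controller data remain if the dose is given at the time of the record.

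**The case against.** The strongest reply has four parts.

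- **The endpoint wording.** The phrase "when on each treatment modality (BPS vs. no BPS" may only identify which session the data come from. Keeping short off-controller spells would then be ordinary all-data practice. That is a fair reading, but it does not explain why the 2 h after an interruption are removed while the interruption is kept.
- **The meaning of following.** It could run from the onset of the interruption, which would cover its first 2 h. This weakens step 3 for interruptions up to 2 h. It leaves the occlusion arithmetic and the loop-off gap untouched.
- **Materiality.** This is an early exploratory study under continuous supervision, and the shifts per event are small. This stands, and it limits the weight of the point.
- **The 80% rule has a purpose.** Meals are matched between days, and a session with a large hole may miss a meal response that its pair contains. This also stands. It is the reason not to count availability before the removals: an occlusion recorded at 10:00, a syringe dose at 10:30 and closed loop back at 14:30 would then pair an 11.5 h session with an 18 h one.

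A reader might also infer more than the documents support:
- That one occlusion wastes the whole session. It does not: 24 h TIR is still computed, and so are meal and overnight outcomes whose windows still pass.
- That every occlusion treated by syringe contaminates the primary endpoint. Mid-window ones cannot, because the session is void.
- That occlusions may go unrecorded. Section 14.1 says that "electronic device files and electronic CRFs are considered the primary source documentation".
- That a 24 h primary is affected in the same way. The synopsis does state 24 h, and there a single occlusion would pass; the statistical sections use daytime.

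**Conclusion.** The point holds and is worth correcting, at modest weight. Under 13.3.1, 13.3.3 and 13.3.4 as written, a single occlusion recorded more than 1.6 h inside the daytime window edges leaves between 77.8% and just under 80% of readings, and that session has no primary outcome. If that loses the pair, the detectable difference rises from 7.9 to 8.2 points for one pair and 8.7 for three.

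The off-controller data that are kept matter less: about 3% to 9% of the retained daytime for interruptions of 1 to 2 h, and up to 22% of the window after non-pump insulin with no occlusion record. Each event moves the 20-pair mean by about 1 point at most.

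This rests on the 18 h daytime primary, on complete-pair analysis, on two-sided 0.05, and on 12% as the SD of the difference. No event rate is given, so the expected number of affected sessions cannot be stated. Nothing in the documents supports a bias in a known direction: the same rules apply in both BPS states. Nor does every infusion-site failure lead here. One fixed by a site change need not bring the 4 h loop-off.

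**What to change.** 1. **13.3.3, identically for both BPS states and from the DiAs log:** remove CGM from the start of any pump/DiAs interruption longer than 1 h until 2 h after it ends, and from any non-pump insulin dose until closed loop resumes.
2. **13.3.4:** keep the test after data treatment, and keep 80% for the 24 h, meal and overnight windows. Set 75% for the 18 h daytime primary. This allows 4.5 h of loss, so one occlusion (77.8% left) no longer voids the session. Do not move the test ahead of the removals.
3. **Sensitivity analysis:** rerun the primary model once with all CGM kept and all sessions included. Report hours analysed and percent closed-loop time by BPS state beside it.

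Items 1 and 2 belong together. Under item 1 an interruption of L hours leaves 1 − (L + 2)/18, which falls below 80% once L exceeds 1.6 h but stays at or above 75% up to L = 2.5 h.

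The cost is a few sentences and one extra model run; closed-loop time is already planned in 13.6. There are two downsides. A retained session may cover up to 4.5 fewer daytime hours than its pair. Longer off-controller periods will still void a session: in the 10:00 example, 6.5 h are removed and 11.5/18 = 63.9% remain. The all-CGM rerun checks both.
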